## 10.3.3 Pain and Quality of Life Analyses

Pain will be assessed by a:

• NRS at Screening, and Visits V1, V4, V6, V10, V16 (EOT), and Ob2

and quality of life by the:

• Dermatology Life Quality Index score at Screening, and Visits V1, V4, V6, V10, V16 (EOT), and Ob2

Basic descriptive statistics (e.g., number of observations (n), mean, standard deviation, minimum, median, maximum, lower quartile, upper quartile) will be displayed for the absolute values by visit and for the change of baseline at each visit for each scale.

The number and percentage of subjects in each answer category will be displayed for each of the 10 Dermatology life quality index items.

All analyses will be conducted on the SAF. Analyses will generally be performed for the entire SAF as well as the 3 dosing groups separately. Additional stratifications based on actual dosing and IMP compliance will be defined in the statistical analysis plan.

## 10.3.4 Analyses of Concentrations of IFX-1

Concentrations of IFX-1 will be summarized by time point. Derived parameters will be analyzed by displaying basic statistics (e.g., number of observations (n), mean, standard deviation, coefficient of variation, minimum, median, maximum, geometric mean, geometric coefficient of variation). All concentration parameters will be analyzed on the SAF including all values and subjects that are assessed as evaluable by the pharmacokinetic specialist. Analyses will generally be performed for the entire SAF as well as the 3 dosing groups separately. Additional stratifications based on actual dosing and IMP compliance will be defined in the statistical analysis plan.

#### 10.3.5 Other Analyses

The following parameters will be analyzed descriptively as exploratory endpoints on the SAF.

Safety parameters:

• Safety laboratory parameters will be analyzed by displaying basic summary statistics (e.g., for continuous variables, number of observations (n), mean, standard deviation, minimum, median, maximum, lower quartile, upper quartile) for absolute values and changes from baseline by visit.

- Anti-drug antibody from blood samples at time points described in the Schedule of Assessments will be analyzed by the number and percentage of subjects presenting anti-drug antibody as per time point.
- The number of subjects with abnormal physical examination parameters will be displayed by visit.
- Immunology and other assessments on blood, ulcer fluid, biopsies, and stools will be analyzed by displaying basic summary statistics.

## 10.3.6 Interim Analyses

Interim analyses will be performed after each initial dosing group of 6 subjects has completed Visit V10. The interim analysis will comprise adverse events, Physician's Global Assessment, and photographic documentation of area and volume.

Statistics for the above parameters will be generated as for the final analysis.

The statistical analysis plan will describe the planned interim analyses in detail.

# **12 APPENDICES**

InflaRx	Clinical Study Protocol,
	Version 4.0 Including Amendment 02, 14 May 2020
IFX-1	IFX-1-P2.7

# Appendix 1 Safety Laboratory Tests

The tests detailed in Table 2 will be performed by a local laboratory. Protocol-specific requirements for inclusion or exclusion of subjects are detailed in Section 29 of the protocol. Additional tests may be performed at any time during the study as determined necessary by the investigator or required by local regulations.

Investigators must document their review of each laboratory safety report.

Assessment
Parameters

Hematology
Image: Clinical chemistry and the second secon

 Table 2
 Protocol-Required Safety Laboratory Assessments

InflaRx	Clinical Study Protocol,
	Version 4.0 Including Amendment 02, 14 May 2020
IFX-1	IFX-1-P2.7

# Appendix 2Regulatory and Ethical Considerations

### **Regulatory and Ethical Considerations**

This study will be conducted in accordance with the protocol and with the following:

- Consensus ethical principles derived from international guidelines including the Declaration of Helsinki and Council for International Organizations of Medical Sciences (CIOMS) International Ethical Guidelines
- Applicable International Council for Harmonisation Guidelines for GCP
- Applicable laws and regulations

The protocol, protocol amendments, informed consent form (ICF), investigator's brochure, and other relevant documents (e.g., advertisements) must be submitted to an IRB by the investigator and reviewed and approved by the IRB before the study is initiated.

The study can only start after obtaining a positive evaluation by the applicable IRB and approval from the applicable regulatory authority. The written approval of the applicable IRB and the responsible regulatory authority must be filed in the trial master file. Additionally, each study site must receive a copy of these documents to be filed in the investigator site file.

Any amendments to the protocol will require IRB approval before implementation of changes made to the study design, except for changes necessary to eliminate an immediate hazard to study subjects.

The investigator will be responsible for the following:

- Providing written summaries of the status of the study to the IRB annually or more frequently in accordance with the requirements, policies, and procedures established by the IRB
- Notifying the IRB of SAEs or other significant safety findings as required by IRB procedures
- Providing oversight of the conduct of the study at the site and adherence to requirements of 21 CFR, ICH guidelines, the IRB, European regulation 536/2014 for clinical studies (if applicable), and all other applicable local regulations

#### **Financing and Insurance**

The study is financed by the sponsor.

The subjects are covered by an applicable insurance policy for participation in a clinical study. A copy of the insurance policy and the insurance conditions will be filed in the investigator site file.

InflaRx Clinical Study Protocol, Version 4.0 Including Amendment 02, 14 May 2020 IFX-1 IFX-1-P2.7

### **Financial Disclosure**

Investigators and sub-investigators will provide the sponsor with sufficient, accurate financial information as requested to allow the sponsor to submit complete and accurate financial certification or disclosure statements to the appropriate regulatory authorities. Investigators are responsible for providing information on financial interests during the course of the study and for 1 year after completion of the study.

### **Informed Consent Process**

The investigator or his/her representative will explain the nature of the study, the purposes, the procedures involved, the expected duration, the potential risks and benefits involved, and any discomfort it may entail to each study subject or his/her legally authorized representative and answer all questions regarding the study.

Subjects must be informed that their participation is voluntary. Subjects will be required to sign a statement of informed consent that meets the requirements of 21 CFR 50, local regulations, ICH guidelines, Health Insurance Portability and Accountability Act (HIPAA) requirements, where applicable, and the IRB and study site.

The informed consent must be given by means of standard written statements, written in nontechnical language. The subjects should read the informed consent form and consider their decision before signing and dating the document. A copy of the signed document must be given to the subject. No subject can be involved in the study if he/she is related to the investigator, any member of the team at the study site, or the sponsor.

The medical record must include a statement that written informed consent was obtained before the subject was enrolled in the study and the date the written consent was obtained. The authorized person obtaining the informed consent must also sign the ICF.

Subjects must re-consent to the most current version of the ICF during their participation in the study.

A copy of the ICF must be provided to the subject.

Subjects who are rescreened are required to sign a new ICF.

Subjects will need to consent to photographical documentation of affected areas.

#### **Data Protection**

Subjects will be assigned a unique identifier by the sponsor. Any subject records or datasets that are transferred to the sponsor will contain the identifier only; subject names or any information which would make the subject identifiable will not be transferred.

InflaRx Clinical Study Protocol, Version 4.0 Including Amendment 02, 14 May 2020 IFX-1 IFX-1-P2.7

The subject must be informed that his/her personal study-related data will be used by the sponsor in accordance with local data protection law. The level of disclosure must also be explained to the subject.

The subject must be informed that his/her medical records may be examined by Clinical Quality Assurance auditors or other authorized personnel appointed by the sponsor, by appropriate IRB members, and by inspectors from regulatory authorities.

The sponsor will ensure that all safeguards are in place to minimize any eventual risk of breaches, and complies otherwise with the requirements of European Union General Data Protection Regulation (GDPR, Regulation (EU) 2016/679). The sponsor will regularly check all procedures relevant to the processing of personal data, as to ensure privacy by design and compliance with GDPR.

## **Publication Policy**

The results of this study may be published or presented at scientific meetings. If this is foreseen, the investigator agrees to submit all manuscripts or abstracts to the sponsor before submission. This allows the sponsor to protect proprietary information and to provide comments.

The sponsor will comply with the requirements for publication of study results. In accordance with standard editorial and ethical practice, the sponsor will generally support publication of multisite studies only in their entirety and not as individual site data. In this case, a coordinating investigator will be designated by mutual agreement.

Authorship will be determined by mutual agreement and in line with International Committee of Medical Journal Editors authorship requirements.

## **Dissemination of Clinical Study Data**

The sponsor will provide the relevant study protocol information in a public database (e.g., ClinicalTrials.gov, https://clinicaltrials.gov/) before or at commencement of the study. The sponsor may also provide study information for inclusion in national registries according to local regulatory requirements.

If a potential subject contacts the sponsor regarding participation in the study, the investigator agrees that the sponsor may forward the study site and contact details to the subject. Based on the inclusion and exclusion criteria for the study, the investigator will assess the suitability of the subject for enrollment into the study.

Results of this study will be disclosed according to the relevant regulatory requirements. All publications in peer-reviewed medical journals resulting from this study will be listed in the original study protocol registration record (e.g., on ClinicalTrials.gov).

InflaRx	Clinical Study Protocol,
	Version 4.0 Including Amendment 02, 14 May 2020
IFX-1	IFX-1-P2.7

## Monitoring

Monitoring of the study sites will be performed by a contract research organization designated by the sponsor and will be based on the contract research organization's monitoring standard operating procedures as well as the study specific monitoring manual.

The clinical monitor, as a representative of the sponsor, has the obligation to follow the study closely. The monitor will visit the study site at periodic intervals in addition to maintaining necessary telephone calls and written contact as appropriate. The monitor will maintain a working knowledge of the study through observation, review of study records and source documentation, and discussion of the conduct of the study with the investigator and study site personnel. Source data verification of the eligibility criteria as described in the monitoring manual will be performed for all subjects.

The monitor will report via the project manager of the sponsor-designated contract research organization to the sponsor who carefully monitors all aspects of the study for compliance with applicable government regulations, with respect to current ICH guidelines for GCP and current standard operating procedures.

### Data Quality Assurance

All subject data relating to the study will be recorded on printed or electronic CRF unless transmitted to the sponsor or designee electronically (e.g., laboratory data). The investigator is responsible for verifying that data entries are accurate and correct by physically or electronically signing the CRF.

The investigator must maintain accurate documentation (source data) that supports the information entered in the CRF.

The investigator must permit study-related monitoring, audits, IRB review, and regulatory agency inspections and provide direct access to source data documents.

The sponsor or designee is responsible for the data management of this study including quality checking of the data.

Study monitors will perform ongoing source data verification to confirm that data entered into the CRF by authorized site personnel are accurate, complete, and verifiable from source documents; that the safety and rights of subjects are being protected; and that the study is being conducted in accordance with the currently approved protocol and any other study agreements, ICH GCP, and all applicable regulatory requirements.

Records and documents, including signed ICFs, pertaining to the conduct of this study must be retained by the investigator for 25 years after study completion unless local regulations or institutional policies require a longer retention period. No records may be destroyed during

InflaRx	Clinical Study Protocol,
	Version 4.0 Including Amendment 02, 14 May 2020
IFX-1	IFX-1-P2.7

the retention period without the written approval of the sponsor. No records may be transferred to another location or party without written notification to the sponsor.

### **Source Documents**

Source documents provide evidence for the existence of the subject and substantiate the integrity of the data collected. Source documents are filed at the investigator's site.

Data reported on the CRF or entered in the CRF that are transcribed from source documents must be consistent with the source documents or the discrepancies must be explained. The investigator may need to request previous medical records or transfer records, depending on the study. Also, current medical records must be available.

Source data comprise data in medical records, ECG assessments, and wound assessment records.

#### Audits

In order to guarantee that the conduct of the study is in accordance with ICH guidelines for GCP and the national laws, audits may be performed at the study sites to be carried out by an independent auditor. In addition, for-cause audits may be scheduled.

The investigator agrees to give the auditor access to all relevant documents for review.

## Inspections

According to the corresponding ICH guidelines for GCP, inspections of the study sites may be performed by the local or federal authorities at any time during or after completion of the study.

The investigator agrees to give the inspectors access to all relevant documents for review.

#### Study and Site Closure

The sponsor designee reserves the right to close the study site or terminate the study at any time for any reason at the sole discretion of the sponsor. Study sites will be closed upon study completion. A study site is considered closed when all required documents and study supplies have been collected and a study-site closure visit has been performed.

The investigator may initiate study-site closure at any time, provided there is reasonable cause and sufficient notice is given in advance of the intended termination.

InflaRx	Clinical Study Protocol,
	Version 4.0 Including Amendment 02, 14 May 2020
IFX-1	IFX-1-P2.7

Reasons for the early closure of a study site by the sponsor or investigator may include but are not limited to:

- Failure of the investigator to comply with the protocol, the requirements of the IRB or local health authorities, the sponsor's procedures, or GCP guidelines
- Inadequate recruitment of subjects by the investigator
- Discontinuation of further IMP development

# Appendix 3Adverse Events: Definitions and Procedures for
Recording, Evaluation, Follow-up, and Reporting

#### Definition of an Adverse Event

An adverse event is any untoward medical occurrence in a patient or clinical study subject, whether or not considered related to the IMP.

NOTE: An adverse event can therefore be any unfavorable and unintended sign (including an abnormal laboratory finding), symptom, or disease (new or exacerbated).

Treatment emergent adverse events are adverse events that are temporally associated with the use of IMP.

**Events Meeting the Adverse Event Definition** 

- Any abnormal laboratory test results (hematology, clinical chemistry, or urinalysis) or other safety assessments (e.g., ECG, radiological scans, vital signs measurements), including those that worsen from baseline, considered clinically significant in the medical and scientific judgment of the investigator (i.e., not related to progression of underlying disease).
- Exacerbation of a chronic or intermittent pre-existing condition including either an increase in frequency and/or intensity of the condition.
- New conditions detected or diagnosed after IMP administration even though it may have been present before the start of the study.
- Signs, symptoms, or the clinical sequelae of a suspected drug-drug interaction.
- Signs, symptoms, or the clinical sequelae of a suspected overdose of either IMP or a concomitant medication. Overdose per se will not be reported as an adverse event/SAE unless it is an intentional overdose taken with possible suicidal/self-harming intent. Such overdoses should be reported regardless of sequelae.
- "Lack of efficacy" or "failure of expected pharmacological action" per se will not be reported as an adverse event or SAE. Such instances will be captured in the efficacy assessments. However, the signs, symptoms, and/or clinical sequelae resulting from lack of efficacy will be reported as adverse event or SAE if they fulfil the definition of an adverse event or SAE.

#### Events NOT Meeting the Adverse Event Definition

- Any clinically significant abnormal laboratory findings or other abnormal safety assessments which are associated with the underlying disease, unless judged by the investigator to be more severe than expected for the subject's condition.
- The disease/disorder being studied or expected progression, signs, or symptoms of the disease/disorder being studied, unless more severe than expected for the subject's condition.

InflaRx	Clinical Study Protocol,
	Version 4.0 Including Amendment 02, 14 May 2020
IFX-1	IFX-1-P2.7

- Medical or surgical procedure (e.g., endoscopy, appendectomy): the condition that leads to the procedure is the adverse event.
- Situations in which an untoward medical occurrence did not occur (social and/or convenience admission to a hospital) or planned hospitalizations due to a pre-existing condition that has not worsened (e.g., elective surgery).
- Anticipated day-to-day fluctuations of pre-existing disease(s) or condition(s) present or detected at the start of the study that do not worsen.

#### Definition of an adverse events of special interest

An adverse event of special interest is an adverse event of scientific and medical concern specific to the sponsor's product or program, for which ongoing monitoring and rapid communication by the investigator to the sponsor could be appropriate. Such an event might require further investigation in order to characterize and understand it.

#### The following are defined as adverse events of special interest:

 Infusion-related reactions, including acute and delayed hypersensitivity and anaphylactic reactions during or after IFX-1 infusion All patients should be observed closely during the IFX-1 administration and for 30 minutes after the first 2 infusions. The IV line should remain open during the observation to allow for administration of IV drugs, if necessary. Medication for infusion-related reactions should be available for immediate use. Medical staff have to be trained in resuscitation and immediate intensive care has to be readily accessible in case of severe life-threatening events. Mild to moderate reactions may be treated by slowing or interruption of the infusion, or with supportive treatment. For any potential infusion-related event, the investigator should check for a potentially developing or existing anaphylactic reaction. If an anaphylactic reaction is possible, appropriate immediate actions should be taken according to the severity or stage of the detected anaphylactic reaction as recommended by existing guidelines for the treatment of anaphylactic reactions or, if established at the study sites, according to available standard operating procedures or other algorithms.

#### • Meningitis

If there are signs of meningitis at any time during the study, the IMP should be discontinued if meningitis is confirmed. The patient must be closely monitored and the guidelines for treatment of meningitis should be followed. This includes lumbar puncture, blood culture testing, immediate start of treatment with dexamethasone and intravenous antibiotics (combination therapy with ampicillin and third generation cephalosporin), and a search made for the focus of the infection (e.g., computed tomography or magnetic resonance tomography).

- Meningococcal septicemia
- Invasive infection

InflaRx	Clinical Study Protocol,
	Version 4.0 Including Amendment 02, 14 May 2020
IFX-1	IFX-1-P2.7

All adverse events of special interest will be recorded and reported as SAEs, and subject narratives will be generated. Further information may be requested from the investigator.

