# **Objectives and Endpoints:**

Objectives	Endpoints
Primary	
• Explore the safety of IFX-1 for the treatment of subjects with pyoderma gangrenosum	• Occurrence, nature and intensity of treatment emergent adverse events (TEAEs), related TEAEs, serious TEAEs, and adverse events of special interest
Key Secondary	
• Explore the efficacy of IFX-1 for the treatment of pyoderma gangrenosum	
 
Responder rate defined as Physician's Global Assessment ≤3 of target ulcer at Visits V4, V6, V10, and V16 (End of Treatment [EOT])
 
Time to complete closure of pyoderma
 

	gangrenosum target ulcer (investigator assessment)
• Explore additional clinical outcome parameters in subjects with pyoderma gangrenosum under the treatment with IFX-1	• Percentage change in wound area and wound volume (wound healing) of target ulcer between Visits V1-V4, V1-V6, V6-V10; V10-V16, and V1-V16 (photographic assessment)
	• Rate of change per day in area of target ulcer (photographic assessment)
	• Number of subjects with a decrease in area of target ulcer of 50% or more at Visit V16 (EOT) compared to baseline (photographic assessment)
	• Number of subjects with a decrease in area of target ulcer of 100% at Visit V16 (EOT) compared to baseline (remission) (photographic assessment)
	• Degree of erythema and border elevation of the target ulcer compared to baseline at Visits V4, V6, V10, and V16 (EOT) (investigator assessment)
	• Mean change from baseline in pain assessed by Numeric Rating Scale (NRS) at Visits V4, V6, V10, and V16 (EOT)
	• Mean change from baseline in Dermatology Life Quality Index (DLQI) at Visits V4, V6, V10, and V16 (EOT)

InflaRx	Clinical Study Protocol,
	Version 4.0 Including Amendment 02, 14 May 2020
IFX-1	IFX-1-P2.7

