#### An SAE is defined as any untoward medical occurrence that, at any dose:

- Results in death
- Is life-threatening

Life-threatening in the definition of "serious" refers to an event in which the subject was at risk of death at the time of the event. It does not refer to an event which hypothetically might have caused death, if it were more severe.

• Required inpatient hospitalization or prolongation of existing hospitalization

In general, hospitalization signifies that the subject has been detained (usually involving at least an overnight stay) at the hospital or emergency ward for observation and/or treatment that would not have been appropriate in the physician's office or outpatient setting. Complications that occur during hospitalization are adverse events. If a complication prolongs hospitalization or fulfills any other serious criteria, the event is serious. When in doubt as to whether "hospitalization" occurred or was necessary, the adverse event should be considered serious.

Hospitalization for elective treatment of a pre-existing condition that did not worsen from baseline is not considered an adverse event.

• Results in persistent disability or incapacity

The term disability means a substantial disruption of a person's ability to conduct normal life functions. This definition is not intended to include experiences of relatively minor medical significance such as uncomplicated headache, nausea, vomiting, diarrhea, influenza, and accidental trauma (e.g., sprained ankle) which may interfere with or prevent everyday life functions but do not constitute a substantial disruption.

- Is a congenital anomaly or birth defect
- Other situations:
  - Medical or scientific judgment should be exercised in deciding whether SAE reporting is appropriate in other situations such as important medical events that may not be immediately life-threatening or result in death or hospitalization but may jeopardize the subject or may require medical or surgical intervention to

InflaRx Clinical Study Protocol, Version 4.0 Including Amendment 02, 14 May 2020 IFX-1 IFX-1-P2.7

> prevent one of the other outcomes listed in the above definition. These events should usually be considered serious. Examples of such events include invasive or malignant cancers, intensive treatment in an emergency room or at home for allergic bronchospasm, blood dyscrasias or convulsions that do not result in hospitalization, or development of drug dependency or drug abuse.

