#### Assessment of Intensity

The investigator will make an assessment of intensity for each adverse event and SAE reported during the study and assign it to 1 of the following categories:

- Mild: an event that is easily tolerated by the subject, causing minimal discomfort and not interfering with everyday activities.
- Moderate: an event that causes sufficiently discomfort and interferes with normal everyday activities.
- Severe: an event that prevents normal everyday activities. An adverse event that is assessed as severe should not be confused with a SAE. Severe is a category utilized for rating the intensity of an event; and both adverse event and SAEs can be assessed as severe.
- An event is defined as 'serious' when it meets at least 1 of the predefined outcomes as described in the definition of an SAE, NOT when it is rated as severe.

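### Appendix 3 has every adverse event of special interest recorded as an SAE, so a mild infusion reaction that meets no seriousness criterion could be counted as a serious TEAE

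*Combined protocol and SAP*

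**What the plan says.** Appendix 3 lists four kinds of AESI: infusion-related reactions, meningitis, meningococcal septicemia and invasive infection. The infusion category reads "Infusion-related reactions, including acute and delayed hypersensitivity and anaphylactic reactions during or after IFX-1 infusion", with no severity threshold. The same entry expects milder cases: "Mild to moderate reactions may be treated by slowing or interruption of the infusion, or with supportive treatment". The list closes with the rule "All adverse events of special interest will be recorded and reported as SAEs, and subject narratives will be generated".

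The SAE definition in the same appendix opens "An SAE is defined as any untoward medical occurrence that, at any dose" and then lists death, threat to life, hospitalization, disability and congenital anomaly, plus important medical events by judgment. AESI status is not on the list. Under Assessment of Intensity the appendix adds: "An event is defined as 'serious' when it meets at least 1 of the predefined outcomes as described in the definition of an SAE". It describes the lowest intensity grade as "Mild: an event that is easily tolerated by the subject, causing minimal discomfort and not interfering with everyday activities".

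The primary endpoint in the Synopsis (Objectives and Endpoints) is "Occurrence, nature and intensity of treatment emergent adverse events (TEAEs), related TEAEs, serious TEAEs, and adverse events of special interest". Section 10.3.1 repeats serious TEAEs and AESIs as separate items. It counts as treatment-emergent any adverse event starting at or after the first dose, and tabulates serious TEAEs by subjects and by events.

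**The concern.** Appendix 3 gives two rules for the same event. Under the AESI rule, a mild infusion reaction that settles when the infusion is slowed is recorded as an SAE. Under the outcome-based definition it is not serious. The protocol does not say which rule sets the seriousness entry in the CRF.

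What is at stake is the meaning of one component of the primary endpoint. If the recorded SAE status feeds the serious TEAE tables, those tables mix events that met a seriousness criterion with events that are there only because of their category. The same event then appears under both components. With 6 subjects per dosing group, one such event visibly changes the reported percentage. Section 10.3.6 has adverse events in every interim analysis, with statistics produced as for the final analysis, so the interim tables would carry the same ambiguity.

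**Working it through.** The plan states no figure to reproduce: section 10.1 says there was no formal sample size calculation, and no infusion-reaction rate is given. The check is a comparison of the text, followed by an illustration of size.

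**1. Can an event be an AESI, be mild and meet no SAE criterion?**
- AESI: yes. Any infusion-related reaction qualifies (Appendix 3).
- Mild: yes. The AESI entry foresees mild to moderate reactions.
- SAE outcome: an event that fits the appendix's own description of mild involves none of the listed outcomes. The important-medical-event clause concerns events that endanger the subject or need intervention to prevent a listed outcome, which does not fit an easily tolerated reaction.
- TEAE: yes. An infusion reaction cannot precede the first dose (section 10.3.1).

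So such an event exists under the protocol's definitions, and the two rules classify it differently.

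**2. Which AESIs are affected?** Meningitis, meningococcal septicemia and invasive infection would ordinarily meet an SAE criterion, as would anaphylaxis. Only milder infusion reactions remain.

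**3. Does any text separate the two classifications?** Section 10.3.1 does not name the variable behind the serious TEAE tables, and has no rule for events that are SAEs only through AESI status. No section requires seriousness by the SAE criteria to be captured separately for an AESI.

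**4. Size per affected subject.** Inputs: 6 subjects per group (section 7.1.2) and 18 in total (section 10.1).
- One group: 1/6 = 16.7 percentage points.
- Whole study: 1/18 = 5.6 percentage points.

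**5. Chance of at least one affected subject.** Let r be the assumed per-subject risk of a mild, non-serious infusion reaction over the whole course of up to 15 dosing visits, with subjects independent. The chance is 1 − (1 − r)^n.

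| Assumed r | n = 6 | n = 18 |
|---|---|---|
| 2% | 1 − 0.98^6 = 11% | 1 − 0.98^18 = 30% |
| 5% | 1 − 0.95^6 = 26% | 1 − 0.95^18 = 60% |
| 10% | 1 − 0.90^6 = 47% | 1 − 0.90^18 = 85% |
| 20% | 1 − 0.80^6 = 74% | 1 − 0.80^18 = 98% |

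**6. With seriousness set by the SAE criteria alone.** A mild reaction adds 0 to the serious TEAE count and stays in the AESI count.

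**The case against.** The strongest reply is that the AESI rule only sets a reporting route. Appendix 3 explains AESIs by the need for rapid communication to the sponsor, and its section on SAE reporting makes the faxed SAE page the usual way to send that information. On this reading, recording an event as an SAE means using the SAE page, and seriousness is still judged by outcome. That reading is possible, but it does not cure the text. The rule says recorded as well as reported, and nothing requires a separate seriousness entry. If the CRF does not hold one, a later statistical analysis plan may be unable to recover it.

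Other parts of the reply stand and limit the point:

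- A reader might infer that a mild reaction definitely counts as a serious TEAE. The documents do not say so. Section 10.3.1 names no source variable, and the detailed analysis plan that section 10.3 promises is not available here. Also, the sentence in Assessment of Intensity says when an event is serious, not only when.
- A reader might infer that the serious count loses its meaning altogether. It does not, because most AESI categories would be serious anyway. The Synopsis also groups serious TEAEs by severity, so a mild event would show as mild.
- A reader might infer that dose escalation would be driven by the inflated count. Section 9.4.9 leaves that decision to the sponsor on safety data from at least 5 patients, with no SAE threshold, and every AESI has a narrative.
- The higher assumed rates have no support in the documents. Section 3.2.1 lists related events for 48 + 82 + 12 = 142 treated subjects in three Phase II studies and names no infusion reaction. Zero in 142 would give an upper 95% bound of 1 − 0.05^(1/142) = 2.1%, or 1 − 0.979^6 = 12% for a group of 6. This is only a rough guide: symptoms may have been coded under other terms, the doses planned here go higher, and no such list is given for IFX-1-P2.4.

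**Conclusion.** The conflict within Appendix 3 is real and lies in the current text. A mild infusion reaction that meets no seriousness criterion could be counted as a serious TEAE as well as an AESI, in two separately listed components of the primary safety endpoint. The word is could, because the step from recorded SAE status to the serious TEAE table is an inference.

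The effect per affected subject, 16.7 points in a group and 5.6 points overall, is simple arithmetic. The probability of seeing it depends on a rate that must be assumed. The low end of the range, about 11% for a group of 6 at a 2% risk, is closest to what the earlier studies suggest. The analyses are descriptive, so no hypothesis test is affected, and no numerical escalation rule depends on the count. Recording too many SAEs also loses no safety information. This is a should-fix: a stated rule can misclassify events in a primary endpoint component, and correcting it is cheap.

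**What to change.** Reconcile the AESI rule in Appendix 3 with the SAE definition and the seriousness sentence in the same appendix:

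- **Appendix 3:** AESIs are reported to the sponsor on the SAE form, within the 24-hour timeline of section 9.4.8.1, with a narrative. The CRF seriousness field is set to yes only if a criterion in the SAE definition is met.
- **Section 10.3.1:** the serious TEAE tables, interim and final, use that field, and AESIs have their own table.
- **CRF completion guide:** repeat the instruction, so that seriousness is captured at entry for every AESI.

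The cost is a few sentences in the protocol and the guide, plus a check that the SAE page has a separate seriousness field. Rapid reporting and narratives are unchanged.
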